4.0 OVERSIGHT OF CLINICAL RESPONSIBILITIES

A. Lead Investigator

The Lead Investigator, with assistance from the Co-Lead Investigator and investigative team, is responsible for study oversight, including ensuring human research subject protection. This study will not use any clinical interventions and there are no expected adverse events during the single on-line completion of the surveys. The only expected risk to participants is a loss of confidentiality, which will be minimized by utilizing an encrypted REDCap platform. Any breach of confidentiality will be reported on a protocol deviation form.

B. Data and Safety Monitoring Board (DSMB)

This study is not an intervention trial and will not require a Data and Safety Monitoring Board. The Lead Investigator along with the Co-Lead Investigator and sub-investigators are responsible for adhering to the Data and Safety Monitoring Plan.

C. Quality Assurance (QA) Monitoring

Study monitoring will be conducted on a regular basis using local QA monitors. QA monitors will assess compliance with the protocol, GCP requirements, and other applicable regulatory requirements, as well as document the integrity of the study progress. Areas of particular concern will be protocol adherence, IRB reviews and approvals, and regulatory documents. The monitors will interact with the participating University site staff to identify issues and re-train the site as needed to enhance research quality. QA Reports will be prepared by the monitors following each site visit. These reports will be sent to the investigative team and NIDA CCTN. The investigative site will provide direct access to all study related sites (e.g., research office), source data/documentation, and reports for the purpose of monitoring and auditing by local Node monitors, as well as inspection by local and regulatory authorities. See protocol sections 10.4, 10.10, 10.11, and 10.13.

D. Management of Risks to Participants

Confidentiality

Confidentiality of participant records will be ensured by encryption and secure storage of any documents that have participant identifiers as well as secure computing procedures for entering and transferring electronic data. No identifying information will be disclosed in reports, publications, or presentations.

Information That Meets Reporting Requirements

The e-consent document will specify the types of information that are required for reporting and that the information will be reported as required. These include suspected or known sexual or physical abuse of a child or elders, or threatened violence to self and/or others.

Pregnancy

As there is no medication intervention, pregnancy will not be excluded within the context of this study.

5.0 STUDY SAFETY

Risks:

Breach of confidentiality: As with any study, there is a potential risk of loss of confidentiality. To maintain participant confidentiality, study records and data will be stored in compliance with the International Conference on Harmonization (ICH) guidelines. Participant-reported data will be collected through REDCap, which is HIPAA-compliant and 21 CFR Part 11- ready for audit trails for tracking data manipulation and exports. Emails or text messages between researchers and participants, used in recruitment efforts, will be deleted after information exchange. We will train all study-related personnel to follow HIPAA regulations for research to ensure confidentiality of all data and that the rights of the patients are protected. All data will reside on password-protected encrypted computers, with only the investigators and key members of the research team having access. A variety of other measures will be taken to protect confidentiality, including: We will 1)

assign a unique ID number to each patient, instead of patient names and 2) restrict access to the key linking names and ID numbers to key staff and the PI at each site. Participants will be told that agents of the IRB and QA monitors will be allowed to inspect research records related to this study, if requested.

Emotional Discomfort: The participants may experience some emotional discomfort from answering sensitive and/or personal questions. There is the possibility that the participant will feel bored. The patient's ability to respond to study assessments in the privacy of his/her own home should help in reducing potential emotional discomfort.

Benefits:

Participants may not experience a benefit from participating in this study. Potential benefits include the chance to contribute to a scientific investigation which may benefit other patients like themselves in the future. The risk/benefit ratio is favorable and conduct of the research well justified.

6.0 REGULATORY ISSUES

Reporting of safety concerns to the IRB ad NIDA: The only expected risk to participants is a loss of confidentiality, which will be minimized by utilizing an encrypted REDCap platform. All breaches of confidentiality will be reported to and reviewed by study leadership in regularly scheduled meetings (not to occur more than weekly and less than monthly).

Reporting of IRB action to NIDA: All communications with and actions of the IRB will be kept in a regulatory binder specific for this study. Any protocol changes, amendments, or deviations will be submitted to the IRBs and NIDA and the IRB's actions will then be reported to NIDA. Any other IRB actions will be submitted to NIDA.

Report of changes or amendments to the protocol: All changes and amendments to the protocol will be submitted to the IRBs and NIDA. Only after IRB and NIDA approvals are granted will the changes and amendments be implemented.

Stopping rules: Individual study participants will be informed of their right to discontinue study participation at any time during the study. The PI may discontinue a participant from the study if deemed clinically appropriate. NIDA has the right to discontinue the investigation at any time.

Disclosure of conflict of interest: The investigators have no conflicts of interest.

7.0 DATA MANAGEMENT PROCEDURES

This protocol will utilize a centralized REDCap data capture program. This electronic data capture system (REDCap) will be developed in collaboration by OVN and University of Utah teams to ensure that guidelines and regulations surrounding the use of computerized systems in clinical studies are upheld. Assessments programmed in REDCap will use validation rules, integrity checks, and hard stops as needed to ensure that data are as complete and accurate as possible. See Protocol section 11.4 for additional details.

8.0 DATA AND STATISTICS RESPONSIBILITIES OF THE OVN and UNIVERSITY OF UTAH

The OVN and the University Utah will: 1) develop and apply data management procedures to ensure the collection of accurate and good-quality data, 2) eCRFs for the collection of all data

required by the study, 3) develop data dictionaries for each eCRF that will comprehensively define each data element, 4) prepare instructions for the use of REDCap and for the completion of eCRFs, 5) conduct ongoing monitoring activities on study data collected from all participating sites, and 6) perform data cleaning activities prior to the final study database lock.

9.0 DATA COLLECTION AND ENTRY

Data will be entered by pharmacy staff and participants into eCRFs through REDCap. Data will be entered into REDCap in accordance with the instructions provided during protocol-specific training and guidelines established by the OVN and the University of Utah. Data entry into the eCRFs is performed by authorized individuals. Mentioned above, assessments programmed in REDCap will use validation rules, integrity checks, and hard stops as needed to ensure that data are as complete and accurate as possible. The investigator at the participating University site is responsible for maintaining accurate, complete and up-to-date research records. See Protocol sections 10.4 and 11.9 that provides overviews of Data Quality Assurance and Quality Assurance Monitoring.

10.0 DATA MONITORING, CLEANING, AND EDITING

eCRFs will be monitored for completeness and accuracy throughout the study. Dynamic reports listing missing values and forms are available in REDCap. These reports will be monitored regularly by the OVN and the University of Utah. See Protocol section 11.9 that provides an overview of Data Quality Assurance.

Study progress and data status reports, which provide information on recruitment, availability of primary outcome, regulatory status, and data quality, will be generated regularly and shared with project research leadership and staff.

11.0 DATABASE LOCK AND TRANSFER

At the conclusion of data collection for the study, the OVN and University of Utah will perform final data cleaning activities and will “lock” the study database from further modification. The final analysis dataset will be transferred to the Lead Investigator or designee. De-identified versions of these datasets will also be provided to the NIDA CCTN-designated parties for posting on Datashare, as well as storage and archiving. We will comply with the following policy regarding the preparation and transfer of the study data:

“Data from CTN trials are posted 18 months after the final database lock or after the primary manuscript is published, whichever comes first. All of the data are de-identified, and only raw data (i.e., no analysis datasets or derived variables) are provided. Data documentation, consisting of all annotated case report forms (CRFs), the data dictionary, and de-identification notes, is provided to users to assist in data interpretation. Protocol documentation, including a brief study description, the study protocol, and a link to the primary manuscript, is also provided, and users are encouraged to consult these documents for insight regarding proper interpretation of the data.”

DSM PLAN ADMINISTRATION

Responsibility for data and safety monitoring: the study Lead Investigators will be responsible for the safety monitoring of the study participants.

Frequency of DSM reviews: The study protocol will be reviewed by the CCTN Protocol review Board before recruitment starts. Breaches of confidentiality will be reviewed by study leadership in regularly scheduled meetings for the duration of the study. DSM reports will be submitted to the IRBs and NIDA annually.

Content of DSM report: The DSM report will include a brief description of the study and any changes made. Additionally, we will report baseline sociodemographic characteristics, including age, gender, and race of the subjects screened and randomized. We will also report retention rates and the disposition for all study participants. Any quality assurance issues, regulatory issues, and breaches of confidentiality will be included in the report.

**June 17, 2019**

## 1.0 STUDY DESIGN AND OBJECTIVES

### 1.1 STUDY DESIGN

This study is a one group, cross-sectional, validation study. Approximately 1,523 adults prescribed opioid medications will be recruited from one of 15 participating Kroger Pharmacies. Two sources of data will be obtained for this study. The first source is participants will complete self-report assessments via a secure on-line portal regarding contact; demographic; and behavioral and physical health information. The second source is the Narcotic Score (NS), referred to as the “NS metric” herein, which will be provided by Appriss Health.

### 1.2 STUDY OBJECTIVES

The goal of the study is to validate NS metric as Prescription Drug Monitoring Program-based instrument to discriminate between low, moderate, and high-risk opioid use disorder. The World Health Organization Alcohol, Smoking, and Substance Involvement Screening Test (WHO ASSIST) will be used as the gold standard instrument that defines patient risk levels. No intervention or hypothesis will be tested.

There are 2 statistical Aims in the project:

**Aim 1:** To assess the overall ability of NS metric to discriminate between opioid use risk levels and to determine cut-point thresholds for NS metric total score to classify patients into low, moderate, and high risk groups.

**Aim 2:** To validate the NS metric classifier (with selected cut-point threshold values from Aim 1 as a clinical measure to evaluate patients’ opioid risk level, with WHO ASSIST as the gold standard to which the NS metric is compared.

Other exploratory statistical Aims include:

- To explore the association between NS metric and other indicators of opioid use risk, such as: the Tobacco, Alcohol, Prescription medication and other Substances (TAPS) Tool; a positive misuse indication from the Prescription Opioid Misuse Index (POMI); and history of opioid overdose.
- To collect validity data on the TAPS tool in a large sample of individuals filling opioid pain medications.

## 2.0 GENERAL DEFINITIONS

### 2.1 DEFINITION OF STUDY POPULATION

#### 2.1.1 ALL ENROLLED SUBJECTS POPULATION

The enrolled subjects population (ENR) will contain all participants who provide informed consent for this study and are deemed as meeting the inclusion/exclusion criteria. ENR will be used to summarize subject disposition.

### **2.1.2 COMPLETER POPULATION**

A participant is considered as a completer if all of the participant's electronic Case Report Forms (eCRFs) have been completed, although it is possible that some questions on the eCRFs may not be answered. The completer population will be used as the main analysis population.

## **2.2 DEFINITION OF ASSESSMENTS**

### **2.2.1 NS METRIC**

Appriss Health has developed the NS metric, which uses PDMP data on prescription opioid and benzodiazepine use and aberrant drug behavior (e.g., multiple providers, pharmacies) to compute a score quantifying the extent of the patient's risk in relation to all prescription opioid users. The NS metric is a continuous indicator on a 000-999 scale, with the last digit representing active number of opioid prescriptions (those with  $\geq 9$  prescriptions coded as 9) and the first two numbers representing a composite risk score. Higher scores indicate increased risk for adverse opioid-related outcomes (e.g., overdose). See CTN-0093 Protocol Study Assessments section for details on score composition.

### **2.2.2 WHO ASSIST**

The WHO ASSIST opioid use risk domain will be used as the gold standard to which the NS metric will be compared. The WHO ASSIST opioids domain is a continuous indicator on a 0-20 scale, with the 0-0.5 range representing low risk, the 0.5-14.5 range representing moderate risk, and the 14.5-20 range representing high risk. The WHO ASSIST has demonstrated criterion, construct, concurrent, and discriminant validity.

### **2.2.3 TAPS**

The TAPS Tool consists of a 5-item screening for tobacco use, unhealthy alcohol use, prescription medication misuse, and illicit substance use. Positive reports on the screener result in respondents subsequently being asked 9 additional substance specific items. Scoring on the TAPS Tool involves summing respondents' answers to the substance specific questions, resulting in a 0-3 ordinal score for each drug (0=No use in the past 3 months; 1= problem use; 2= higher risk). The TAPS Tool has demonstrated concurrent validity. This measure will be captured in order to provide additional information regarding its psychometric properties compared to the WHO ASSIST.

### **2.2.4 OTHER MEASUREMENTS**

Covariates known to be correlated with opioid use severity will also be captured. These covariate measures will include: opioid medication misuse, pain severity, general health status, depression, overdose frequency history.

A list of study measurements and domains of interest are summarized in **Table 1**:

**Table 1. Study Measures**

Domain	Name	No. of Items	Min. to Complete
Opioid use severity	WHO Alcohol, Smoking and Substance Involvement Screening Test (ASSIST): Opioid Items 	8	≤5
	WHO Alcohol, Smoking and Substance Involvement Screening Test (ASSIST): Adapted heroin and prescription opioid items 3*	16	≤5
	Tobacco, Alcohol, Prescription Medication, and Other Substance Use (TAPS) 1 / 2 Tool: Prescription drug and prescription opioid items 	2-4	≤1
	Tobacco, Alcohol, Prescription Medication, and Other Substance Use (TAPS) 1 / 2 Tool: Illicit drug and heroin items 	2-4	≤1
Opioid medication misuse	Prescription Opioid Misuse Index 	6	≤5
Opioid overdose	Overdose Experiences, Self and Witnessed—Drug (OESWD) 	1	≤1
Non-opioid drug use severity	WHO Alcohol, Smoking and Substance Involvement Screening Test (ASSIST): Non-opioid drug use items 	8-72	5-15
	Tobacco, Alcohol, Prescription Medication, and Other Substance Use (TAPS) 1 / 2 Tool: Non-opioid items 	12-25	≤5
Depression	Patient Health Questionnaire-2 	2	≤1
Physical Health	Short Form-12: General health subscale 	1	≤1
	Brief Pain Inventory 	8	≤5
Demographics	PhenX demographics: age, education, gender, race, ethnicity, health insurance, employment, marital status	10	<5
		Totals: 76-157	40-50

\* The adapted heroin and prescription opioid items will not be employed in the a priori analyses.

### 3.0 STATISTICAL CONSIDERATION

#### 3.1 MULTICENTER STUDIES

This study will be conducted by multiple investigators at multiple Universities; however, these data will be captured in a single REDCap data system. Descriptive statistics on demographic, other characteristics, and clinical measurements of interests (described in Section 2.2) will be presented by pharmacy recruitment site and between site differences will be examined.

#### 3.2 DATA MANAGEMENT

Throughout the data collection phase of the study, the OVN and University of Utah teams will

collaborate to share a cleaned identified datasets with Appriss Health. Using the patient name, contact information, survey timestamp, and store location; Appriss will deterministically match NS metric data with the final dataset and share a merged dataset with OVN and the University of Utah for analyses. It is important to note that given the privacy of the survey response method (i.e., self-report outside of the pharmacy setting), we anticipate participant responses will have less measurement error (e.g., less social desirability bias). Thus, we anticipate our participant responses will more accurately relate to objective PDMP information than interviewer administered or pharmacy-based surveys.

### **3.3 DISPOSITION**

The number and percentages of screened and enrolled subjects as well as subjects who complete all eCRFs will be presented based on ENR.

### **3.4 DEMOGRAPHIC AND OTHER BASELINE CHARACTERISTICS**

Demographic data and other baseline characteristics will be summarized using descriptive statistics for the Completers Population and ENR. Demographic and other baseline characteristics include, but are not limited to:

- Age (years) - calculated relative to date of submitted e-consent
- Education
- Birth gender
- Race
- Ethnicity
- Health Insurance
- Employment
- Marital status

### **3.5 STATISTICAL METHODS**

The Completer Population will be randomly split into training data set and testing data set with a 1:1 ratio, stratified by WHO ASSIST risk levels. The training data set will be used to select cut-points for NS metric risk levels, and testing data set will be used to address statistical Aim 2, validating the selected cut-points. The proposed approach allows us to assess the predictive ability of the NS metric classifier with an independent testing data set and avoid potentially overfitting. All analyses will be performed both overall and within sex specific subpopulations, to examine sex difference in discrimination, selected cut-points, and agreement between measures.

Summary statistics will be provided for the following clinical assessments for the population, by gender subpopulation, by pharmacy recruitment sites.

- NS Metric
- WHO ASSIST
- TAPS
- OESWD
- Prescription Opioid Misuse Index
- PHQ-2
- SF-12
- Brief Pain Inventory

**Statistical Aim 1 – To assess the ability of NS metric to discriminate between opioid use risk groups and to determine cut-off points for NS metric total score.**

*To assess the ability of NS metric to discriminate between opioid use risk groups:*

The discriminative validity of an instrument concerns its ability to discriminate between known groups. In the project, the known groups are the low risk, moderate risk, and high risk groups as defined by WHO ASSIST opioid domain (0-0.5 range=low risk, 0.5-14.5 range=moderate risk, and 14.5-20 range=high risk).

A receiver operating characteristics (ROC) analysis will be conducted to 1) assess the overall discriminative ability of NS metric score as a clinical risk assessment instrument, 2) select cut-point threshold values to define low, moderate, and high risk groups with NS metric.

Area under the ROC curve (AUC) values will be used to determine the overall discriminating ability of NS metric. AUC is an overall performance measurement for the classification of an instrument at various threshold settings, and it tells how much the classifier is capable of distinguishing between classes. The following scale will be used for the evaluation: <0.70=poor,  $\geq 0.70$ =fair,  $\geq 0.80$  good  $\geq 0.9$ =excellent.

The study will be powered to the least prevalent but most severe condition among potential patients. Based on the allocation ratio of the national rate of prescription opioid use disorder (POUD) among those prescribed opioid medications in the last year, the prevalence of Poud is 2.1%. A sample of approximately 1,523 (32 positive group) achieves 97.68% power to detect a difference of 0.2 between the area under the ROC curve (AUC) under the null hypothesis of 0.5 and the alternative hypothesis of 0.7 using a two-sided z-test at a significance level of 0.050.

The Completer Population (both training and testing set) will be used to assess the overall discrimination ability of NS metric.

*To determine cut-point threshold values for NS total score:*

The objective is to select the optimal cut-points threshold for NS metric to define low, moderate and high risk groups. We will use a hybrid framework where we can make use of the data driven methods to support the clinician's final decision making. Only the training data set will be used in this portion of analysis.

In the first step, the solution space (a subset of optimum choices of cut-point threshold values) will be identified with the following grid search approach: for each pair of risk groups, for example, low risk vs moderate risk, calculate the following performance measurements for each possible cut-point threshold value:

- Sensitivity (SE)

$$SE = \frac{\text{True Positive Rate}}{\text{True Positive Rate} + \text{False Negative Rate}}$$

- Specificity (SP)

$$SP = \frac{\text{True Negative Rate}}{\text{True Negative Rate} + \text{False Positive Rate}}$$

- Positive Predictive Value (PPV): probability that the risk level is present (based on WHO ASSIST) when the result with NS metric is positive.
- Negative Predictive Value (NPV): probability that the risk level is not present (based on WHO ASSIST) when the test result with NS metric is negative.
- Youden's index:

$$\text{Youden's Index} = SE + SP - 1$$

Youden's index, a metric that summarizes both false positive and false negative misclassification rates with equal weights, will be used as primary evaluation criteria to compare classification performance across scenarios with different cut-points threshold values. A solution space, i.e. a set of cut-point threshold values with highest Youden's Index, will be selected. For example, the selected solution space of low risk vs moderate risk cut-point threshold is 10-30, which gives the highest 10% Youden's Index among all possible choices (0-999). See **Table 2** as an example of grid search result:

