**Table 2: Grid search result for threshold value of moderate vs high risks**

Possible Threshold values for high risk vs moderate risk	Youden's Index	SE	SP	PPV	NPV	Rank of Youden's Index	Flag for solution space
0	XXX	XXX	XXX	XXX	XXX		
...							
511	XXX	XXX	XXX	XXX	XXX	10/1000	Yes
512	XXX	XXX	XXX	XXX	XXX	100/1000	Yes
513	XXX	XXX	XXX	XXX	XXX	200/1000	No
...							
999	XXX	XXX	XXX	XXX	XXX		

In the second step, the final optimal cut-points threshold values will be selected from the solution space, with clinical justification such that the balance between sensitivity and specificity is achieved. For example, a cut-off point of 20 is selected for low risk vs moderate risk group based upon clinician's justification. This framework will integrate clinical knowledge into purely data-driven techniques.

Assuming the acceptable SE and SP are 0.8 for both cutoffs (low vs moderate/high and low/moderate vs high), with a sample size of 750 patients in the training data set, the width of 95% confidence intervals of SE and SP estimations are 0.026 and 0.056 for the classification cutoffs that predict low risk vs moderate/high (prevalence 82.9% vs 17.1%). For predicting low/moderate risk vs high risk (prevalence 2.1% vs 97.9%), the width of confidence intervals for SE and SP are 0.143 and 0.024, respectively. The narrow confidence intervals imply relatively high precision for the SE and SP estimations, which will be used to support clinicians' decision making.

The final selected cut-points threshold values will be validated with an independent testing data set in Aim 2.

**Statistical Aim 2 – To validate discriminative ability of NS metric (with the established risk levels of low, moderate, and high) as a clinical measure to evaluate opioid use risk level.**

The second primary aim of the project is to evaluate the concurrent validity of the NS metric with the established risk levels of low, moderate, and high. Classification accuracy will be evaluated with an independent testing data set, and WHO ASSIST will be used as the gold standard to define actual risk levels for patients. The agreement level of risk groups defined by NS metric and WHO ASSIST will be descriptively summarized with a confusion matrix, see **Table 3**. Each row of the matrix represents the instances and percentages in a predicted risk level while each column represents the instances in an actual risk level.

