### 3.6 EXAMINATION OF SUBGROUPS

Subgroup analyses will be conducted on the primary and exploratory aims for the following groups:

- Gender: male and female.

For the subgroup analyses, all completers in each subpopulation will be randomly split into training data set and testing data set with a 1:1 ratio, stratified by WHO ASSIST risk levels. The cut-off threshold values will be selected using similar methods as described in Aim 1 for each subgroup and validated using similar methods as described in Aim 2, with the testing set for the corresponding subgroup. We will compare the selected threshold values and their discriminative ability between subgroups, see **Table 6** for details. *It should be noted* that the study is *not* designed to detect certain agreement level between metrics with high statistical power within any subgroup.

**Table 6. Summary table that compares discrimination ability of NS metrics with established cut-off threshold between 2 gender subgroups, with WHO ASSIST as gold standard.**

		Female	Male	Overall
AUC of ROC	Low risk vs Moderate risk			
	Moderate risk vs high risk			
NS Metric cut-off values	Low risk vs Moderate risk			
	Moderate risk vs high risk			
Validation of selected cut-off values				
Kappa coefficient				
Spearman Correlation Coefficient				
Goodman and Kruskal's Gamma				
Kendall rank correlation coefficient				
Odds ratio from ordinal logit regression				

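### Aim 1 is sized on cumulative splits of the risk groups, but the cut-point measures are specified by pair of groups, and the SAP does not say which governs

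*SAP*

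**What the plan says.** Planning is cumulative.

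- Power (SAP 3.5, Aim 1): "A sample of approximately 1,523 (32 positive group) achieves 97.68% power" for an AUC of 0.7 against 0.5, so the comparison group is the other 1,491 patients. Protocol 9.2.2 gives the same allocation as 46.6 to 1.
- Precision (SAP 3.5, paragraph after Table 2): sensitivity (SE) and specificity (SP) of 0.8 are assumed "for both cutoffs (low vs moderate/high and low/moderate vs high", with prevalences 82.9% vs 17.1% and 2.1% vs 97.9% and 750 training patients. The lower-cut widths are given as "0.026 and 0.056 for the classification cutoffs that predict low risk vs moderate/high"; the upper-cut widths are 0.143 (SE) and 0.024 (SP).

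The analysis is worded by pair.

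- Grid search (SAP 3.5, Aim 1): "for each pair of risk groups, for example, low risk vs moderate risk, calculate the following performance measurements". SE, SP, PPV, NPV and Youden's index follow in the list.
- Table 6 has AUC rows for the two adjacent pairs, one of them "Moderate risk vs high risk".
- In Appendix 1, the ROC curves (Figures 3.1-3.4 and 3.11-3.14) and Table 3.27 describe discrimination or classification of high vs moderate and moderate vs low.

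Other places are ambiguous. Table 2 is headed "Possible Threshold values for high risk vs moderate risk", which may only name a threshold, and the same holds for the titles of Aim 1 Tables 3.7-3.10 and Figures 3.19-3.26. Aim 1 Tables 3.5-3.6, which summarise the AUC, name no contrast.

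**The concern.** Two programmers could both claim to follow the SAP and produce different results. One would subset to the two named groups for each cut; the other would keep everyone and split at the cut. SE, SP, PPV, NPV and AUC would differ.

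This matters at the upper cut (high vs moderate), because the low-risk group left out of that pair is 82.9% of the sample. The SAP says of its planned intervals that "The narrow confidence intervals imply relatively high precision for the SE and SP estimations" and that these estimates will support the clinicians' choice of cut-points. If that choice is made from two-group displays, the stated specificity precision does not describe them. Nor would the PPV shown match the SAP's definition, "probability that the risk level is present (based on WHO ASSIST) when the result with NS metric is positive", for the patients on whom the score will be used. Finally, no output is identified as the AUC to which the 97.68% applies.

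**Working it through.** **Inputs (SAP 3.5).** N = 1,523 with 32 high risk; training n = 750; high 2.1%; moderate/high 17.1%; low 82.9%; SE = SP = 0.8. Moderate alone follows by subtraction: 17.1% − 2.1% = 15.0%.

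**Group sizes.** Training: high 0.021 × 750 = 15.75; moderate 112.5; low 621.75; low + moderate 734.25; moderate + high 128.25. Full sample: high 32, moderate 0.150 × 1,523 = 228, all others 1,491.

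**1. Stated power.** Power = Φ((0.2 − 1.96·SE0)/SE1), where SE0 and SE1 are the standard errors of the AUC under the null and the alternative. The Obuchowski variance is V/n₊, with V = 0.0099·exp(−A²/2)·[(5A² + 8) + (A² + 8)/R], A = √2·Φ⁻¹(AUC) and R = n₋/n₊.

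- 32 vs 1,491: SE0 = 0.0503, SE1 = 0.0507, power 97.7% (SAP: 97.68%).
- 32 vs 228 (high vs moderate only): SE0 = 0.0531, SE1 = 0.0530, power 96.5%.
- If the true AUC is 0.65: 84.5% vs 80.5%.

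**2. Stated widths.** All four reproduce on one scale, the one-sided 95% exact (Clopper-Pearson) upper limit minus 0.8:

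| n | group | result | SAP |
|---|---|---|---|
| 622 | low | 0.0261 | 0.026 |
| 128 | moderate + high | 0.0563 | 0.056 |
| 15 | high | 0.1432 | 0.143 |
| 734 | low + moderate | 0.0240 | 0.024 |
| 112 | moderate only | 0.0600 | none |

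The second and fourth rows decide the matter. A pairwise calculation would have used 112 in both and given 0.060, so the planning basis is cumulative.

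**3. Upper-cut specificity if pairs are literal.** Full two-sided exact 95% width at SP 0.8: n = 734 gives 0.0592 and n = 112 gives 0.1557, a ratio of 2.6.

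**4. Upper-cut PPV if pairs are literal.** High-risk prevalence within the pair is 0.021/0.171 = 12.3%, against 2.1% overall. Let TP be the true positives, F the moderate-risk false positives and k the number of low-risk training patients above the cut. The pair PPV is TP/(TP + F) and the all-patient PPV is TP/(TP + F + k), so the pair value is too high whenever k > 0.

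The documents give neither F nor k. As an illustration only, assume SE 0.8 and SP 0.8 among moderate patients: TP = 0.8 × 15.75 = 12.6 and F = 0.2 × 112.5 = 22.5. The pair PPV is 12.6/35.1 = 35.9%. In all patients:

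| assumed low-risk SP | k | PPV |
|---|---|---|
| 0.80 | 124 | 7.9% |
| 0.90 | 62 | 13.0% |
| 0.95 | 31 | 19.0% |
| 0.99 | 6 | 30.5% |
| 0.994 (equal-variance normal model, SE = SP = 0.8 at both cuts) | 3.6 | 32.6% |

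The pair PPV is halved when k is about 35, which is 35.1/621.75 = 5.6% of low-risk training patients.

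**5. Lower cut.** PPV in the pair is 0.8 × 0.150/(0.8 × 0.150 + 0.2 × 0.829) = 42.0%. In all patients it is 0.8 × 0.171/(0.8 × 0.171 + 0.2 × 0.829) = 45.2%. There is no inflation.

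**6. Youden's index at the upper cut.** Its standard error is √(0.16/15.75 + 0.16/n₋): 0.102 with n₋ = 734.25 and 0.108 with n₋ = 112.5, about 6% larger.

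**The case against.** The strongest reply is that the pair labels simply name a boundary. In a three-level ordered classifier the cut between moderate and high is naturally called that. Most of the shell titles refer to a threshold, and the cut-point shells list the whole training set as their population (Figures 3.1-3.4 list the whole completer population). No sentence says that the third group is dropped. The same subsection names the two cutoffs cumulatively, and the PPV definition fits a cumulative split.

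Much of this stands. It is why threshold-titled shells should not be counted as evidence of pairwise analysis, and why the 112-patient denominator is conditional. It does not settle the matter, because the grid-search sentence is the operating instruction and asks for the measures by pair. Table 6's AUC rows, the ROC figures and Table 3.27 also speak of discriminating or classifying two groups.

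A second reply concerns PPV. The SAP's SP of 0.8 refers to low and moderate patients pooled, not to moderate patients alone. This is correct. If pooled SP is held at 0.8 and low-risk SP is 0.85, moderate SP is (0.8 × 734.25 − 0.85 × 621.75)/112.5 = 0.52. The pair PPV is then 19.0%, against 7.9% in all patients. The 35.9% is therefore one assumed case.

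Third, selection rests on Youden's index, which does not depend on prevalence and whose uncertainty at the upper cut comes mainly from about 15 high-risk patients on either reading. That also stands.

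**Conclusion.** The inconsistency is real and should be clarified. Power and precision are planned on cumulative splits; the instruction for the performance measures, and some displays, are by pair; nothing reconciles them.

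If pairs are literal, upper-cut specificity has a full exact 95% width of 0.156 rather than 0.059 at SP 0.8, and upper-cut PPV is taken at 12.3% rather than 2.1% prevalence. The direction of the PPV error is certain once any low-risk patient exceeds the cut. Its size is not determined: under the illustrative assumptions it is 36% against 8% to 33%. These figures rest on the SAP's planning prevalences and 750 training patients.

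Three stronger conclusions might be inferred and are not supported:

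- That the study loses its power. At AUC 0.7 the pairwise figure is still 96.5%.
- That the chosen cut-points would be unreliable for this reason. The standard error of Youden's index rises by only about 6%, and the Aim 2 confusion matrix and kappa use all three groups, although only after the cuts are fixed.
- That the SAP commits to dropping the low-risk patients, or inflates PPV by a known factor. The first depends on a reading that the SAP leaves open, the second on a low-risk specificity that it does not give.

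**What to change.** 1. In SAP 3.5, replace the pair instruction with the two contrasts that the precision paragraph already assumes, low vs moderate/high and low/moderate vs high, and state the positive and negative group for each cut.
2. Compute SE, SP, PPV and NPV of every candidate cut on the full training set.
3. Name high vs low/moderate as the reported AUC to which the 97.68% applies, and show it in Aim 1 Tables 3.5-3.6.
4. Retitle Table 6 and the Aim 1 shells to match. Adjacent-pair results may be kept as a supplement.
5. If adjacent pairs are instead kept as the main analysis, restate the upper-cut specificity precision for about 112 patients and the power for 32 vs about 228, and still report PPV and NPV on all training patients.

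The cost is SAP and shell wording plus a few lines of code. No new data are needed and the sample size does not change.
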